9.2.3 Analysis Sets

DLT-Evaluable Set will include all patients in dose escalation who have received at least one dose of FT-2102 and completed at least 75% of doses in the first cycle during the DLT evaluation period, or have discontinued due to adverse events meeting the DLT evaluation criteria. This set will be used for DLT analyses only, unless otherwise specified.

Safety Analysis Set will include all patients who have received at least one dose of study drug (FT-2102, azacitidine, or cytarabine). All safety analyses will be based on the Safety Set unless otherwise specified. Patients will be analyzed under the first dose level received by the patient.

Full Analysis Set (FAS) will include all patients who were enrolled in the study and received at least one dose of FT-2102. This analysis set will be used for efficacy analyses. Patients will be analyzed under the assigned dose.

Efficacy Evaluable (EE) Set will include all patients in Phase 2 Cohort 1 with confirmed IDH1-R132 (by central lab) who have received the first dose of FT-2102 at least 6 months prior to the analysis cutoff date or who have died, progressed, or discontinued study participation. This analysis set is the primary set for the Phase 2, Cohort 1 efficacy evaluation. Patients will be analyzed by assigned dose.

Per Protocol (PP) Analysis Set is a subset of patients in the EE set, excluding patients who have protocol violations that could impact the evaluation of the efficacy of FT-2102. Some violations that would result in exclusion from the PP Analysis Set are: not meeting all inclusion/exclusion criteria for a particular cohort, having received chemotherapy not per protocol, received starting dose of FT-2102 other than 150 mg BID, not having at least one post-baseline response assessment. The full list of protocol violations will be reviewed on a de-identified basis by the medical, data management, and statistical leads prior to locking the database, and membership in the PP Analysis Set will be documented and determined based on that review.

PK Analysis Set consists of patients for whom it is possible to calculate at least one primary PK parameter (e.g. C_{max}, AUC_{last} and AUC_{inf}) and who do not have any major protocol deviations thought to influence the absorption, distribution, metabolism and excretion of the FT-2102.

PD Analysis Set consists of all patients who have received at least one dose of FT-2102 and have completed at least one PD assessment. The PD Analysis Set will be used for PK/PD-related analyses unless otherwise specified.

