- Cohort 6 (FT-2102 in combination with azacitidine): approximately 44 patients with R/R AML/MDS that have been previously treated with SA IDH1 inhibitor therapy as their last therapy prior to study enrollment. The actual number of patients in this cohort may be larger, since patients from FT-2102 SA cohorts are allowed to enroll in Cohort 6 after their disease progression.
- Cohort 8 (FT-2102 in combination with azacitidine): approximately 28 treatment naïve AML patients who are candidates for azacitidine first line treatment.

Note that for Cohorts 7 and 8, treatment naïve is defined as no prior treatment for AML. Patients may have received a prior treatment for another hematologic malignancy.

The primary analysis will occur when approximately 190 patients in Phase 2 Cohort 1 have completed 6 months of treatment or discontinued study drug.

B. Study Population

The study will include patients with pathologically proven AML or intermediate risk, high risk or very high risk MDS as defined by the World Health Organization (WHO) criteria or Revised International Prognostic Scoring System (IPSS-R) harboring IDH1-R132 mutations, that is either relapsed or refractory to standard therapy, or for whom standard treatments are contraindicated. Patients must have documented IDH1-R132 gene-mutated disease and must be \geq 18 years of age. See protocol section 4.4 Eligibility Criteria for details.

C. Sample Size

Phase 1

The number of patients who will be enrolled in the dose escalation stage will depend on the number of DLTs observed within each dose cohort. It is anticipated that, at a minimum, doses of 150 mg and 300 mg FT-2102 QD will be tested as a single agent and in combination with azacitidine. If 6 patients are treated at each dose level, approximately 24 patients will be treated in the dose-escalation stage.

During the Phase 1 Dose-Expansion Stage, each of the non-LDAC cohorts would have 14 patients. With 20 patients treated (at least 6 from the dose-escalation stage, 14 from dose-expansion) at the determined MTD/MED there is 90% power of observing adverse events whose true incidence rate is 11% or higher. For the LDAC cohort, the selection of 6 patients is a minor variation of the traditional 3+3 design in order to identify the risk of LDAC for toxicities in more than 17% of patients.

Phase 2

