Cohort 1 (patients with R/R AML harboring IDH1-R132 mutations): A group sequential design is planned for this cohort with two interim analyses and a final test. One hundred

seventy-three (173) patients provide 90% power to test the null hypothesis that the true complete response rate (CR + CRh) is 15% or less versus the one-sided alternative hypothesis that the true complete response rate is greater than 15%, assuming a true response rate of 25%, with a 2.5% significance level using a one-sided exact test for a binomial proportion.

Two interim analyses are planned, at approximately 33% and 67% of the information, respectively. O'Brien-Fleming stopping boundaries will be used for both alpha and beta adjustments. At the first interim, if $\leq 6/58$ responses are observed (or crude p-value ≥ 0.88), the trial may be stopped early for futility. Interim analysis 1 spends 0 alpha and 0.004 beta. The first interim analysis will be conducted on the full analysis set (FAS) within Phase 2 Cohort 1. At the first interim analysis the study is not intended to stop for efficacy. At the second interim analysis, if $\geq 28/115$ responses are observed (or crude p-value is ≤ 0.0057), the trial may stop enrollment for efficacy and if there are 20 or fewer responses (or crude p-value is ≥ 0.2718) the trial will be stopped for futility. Interim analysis 2 spends 0.006 alpha and 0.044 beta. The second interim analysis will be conducted in the efficacy evaluable (EE) analysis set within Phase 2 Cohort 1.

In the event of an early stop for efficacy, all enrolled patients would remain on treatment and their long-term efficacy data, such as, EFS and OS, will continue to be observed.

If the study is not stopped early for efficacy or futility, at least 173 evaluable patients are planned to be enrolled. A one-sided exact test will be performed. If the one-sided p-value is \leq 0.0245, the null hypothesis (the response rate is \leq 15%) will be rejected, and the alternative hypothesis that the response rate is > 15% will be accepted. If exactly 173 patients are evaluable, this is equivalent to 36 or more responses observed.

To account for discordance between central and local testing of the IDH1-132 mutation, approximately 190 patients are planned to be enrolled into this cohort.

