All patients in Phase 2, Cohort 1 with confirmed IDH1-R132 (by central lab) who have received the first dose of FT-2102 180 days or more prior to the analysis cutoff date. These patients will be included in the analysis set regardless of duration of treatment. This analysis set is the primary analysis set for Phase 2, Cohort 1 efficacy evaluation and early stopping decisions. Patients will be analyzed by assigned dose. Patients who received first dose of FT-2102 less than 180 days prior to the analysis cut off date will not be included in the EE Set, even if they have response assessments recorded. Patients who do not have any response data will be considered to be non-responders if they received the first dose of FT-2102 180 days or more before the analysis cut off date. Analyses based on the EE analysis set will not be produced for the final CSR.

5. Per Protocol (PP) Analysis Set

A subset of patients in the EE analysis set, excluding patients who have protocol violations that could impact the evaluation of the efficacy of FT-2102. Some violations that would result in exclusion from the PP analysis set are: not meeting all inclusion/ exclusion criteria for a particular cohort, having received chemotherapy not per protocol, received starting dose of FT-2102 other than 150 mg BID, not having at least one post-baseline response assessment. The full list of protocol violations will be reviewed on a de-identified basis by the medical, data management, and statistical leads prior to locking the database, and membership in the PP analysis set will be documented and determined based on that review. Analyses based on the PP analysis set will not be produced for the final CSR.

6. PK Analysis Set

All patients for whom it is possible to calculate at least one primary PK parameter (e.g. C_{max} , AUC_{last} and AUC_{inf}) and who do not have any major protocol deviations thought to influence the absorption, distribution, metabolism and excretion of the FT-2102.

PK parameters for patients who discontinue after a single dose of study drug may be presented in the listings but will not be used for summary statistics or any statistical analysis. Data may be excluded from PK analysis (concentrations listed only) if any of the following criteria are fulfilled:

- concomitant medication which could render the plasma concentration-time profile unreliable
- Patient vomits within 2 x the reported median T_{max} for the study drug.

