The overall survival and event-free survival analyses will be based on patients in the FAS. All other efficacy analyses will be based on patients in the EE analysis set as the primary analysis, with selected analyses on the FAS and PP analysis set as supportive. The following table indicates the analysis sets to be analyzed for each endpoint.

		A	alysis S	et
Endpoint	Patients Analyzed	EE*	FAS	PP*
CR/CRh Rate,				
DCR/CRh, TTCR/CRh	AML only	Х	Х	Х
CRR, DCR, TTCR	Each disease group separately	х	Х	Х
ORR, DOR, TTR	Each disease group separately	х	Х	х
Best overall Response	Each disease group separately	х	Х	Х
4-month RFS Rate	Phase 2 Cohort 2 only		Х	
RFS	Phase 2 Cohort 2 only		Х	
EFS, OS	All patients combined		Х	
TI	All patients combined	х	х	

*EE and PP analyses will only be performed for IA2.

CR/CRh rate will be analyzed for all cohorts except Phase 2 Cohort 2. For Phase 2 Cohort 1, to test the hypothesis that the CR/CRh rate is greater than 15%, a 1-sided exact test for a binomial proportion will be performed. If the exact one-sided p-value is less than 0.0245, the alternative hypothesis will be accepted. This is equivalent to at least 36 CR/CRh responses of 173 EE patients.

For Phase 2, Cohorts 3, 4, and 5 test the hypothesis that the 85% confidence interval for the CR/CRh rate does not include 10%. If there are 5 or more CR/CRh responses of the 20 patients in these cohorts, the 85% confidence interval will be greater than 10%, and the alternative hypothesis that the response rate is greater than 10% will be accepted.

Phase 2 Cohorts 6, 7, and 8 are Simon 2-Stage designs and the primary efficacy endpoint will be evaluated via the number of CR/CRh responses stipulated in the design criteria described in Section IV.C.

The number and proportion of patients achieving CR/CRh response will be reported by cohort from the binomial proportion, along with Clopper-Pearson 95% confidence interval for AML and MDS patients respectively. Appendix 2 provides the SAS code.

For Phase 2 Cohort 1, a sensitivity analysis will be performed on the CR/CRh rate in which Atkinson and Brown confidence intervals will be calculated.

4-Month RFS, BOR, ORR, TI: The proportional endpoints listed here will be summarized as the number and percentage of patients within each category, and will be presented by cohort along with Clopper-Pearson 95% confidence intervals. The 4-month RFS endpoint will be analyzed for Phase 2 Cohort 2 only.

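### The SAP requires the final Cohort 1 test on the EE set but limits EE to IA2, and the stated p-value limits do not match 36/173

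*Protocol*

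**What the plan says.** **Final test.** SAP VI.I.4 makes EE the primary set for Cohort 1 efficacy and for early stopping. SAP IV.C plans a final exact test if the study is not stopped early: "If exactly 173 patients are evaluable, this is equivalent to 36 or more responses observed". SAP XI.B repeats the rule and attaches it to EE: "This is equivalent to at least 36 CR/CRh responses of 173 EE patients".

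**Limits on EE.** SAP VI.I.4 adds: "Analyses based on the EE analysis set will not be produced for the final CSR". The footnote to the endpoint table in XI.B says "EE and PP analyses will only be performed for IA2". XI.B keeps EE as the primary analysis for response endpoints, "with selected analyses on the FAS and PP analysis set as supportive".

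**Timing.** SAP IV.A states: "The primary analysis will occur when approximately 190 patients in Phase 2 Cohort 1 have completed 6 months of treatment or discontinued study drug". It names no analysis set there, and does not say how this analysis relates to IA2.

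**p-value limit for the final test.** Protocol 9.2.2.2 and SAP IV.C use a one-sided p of at most 0.0245. SAP XI.B uses less than 0.0245. Protocol 9.2.4.3 uses less than 0.023. All four pair the limit with 36 of 173.

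**EE membership.** Protocol 9.2.3 and the synopsis admit centrally confirmed Cohort 1 patients first dosed "at least 6 months prior to the analysis cutoff date or who have died, progressed, or discontinued study participation". SAP VI.I.4 has no such alternative: patients dosed "less than 180 days prior to the analysis cut off date will not be included in the EE Set".

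**The concern.** Read literally, the SAP both requires and rules out the same analysis. If IA2 gave a continue result, the team would reach the final test with its primary set barred from the report and only a supportive set in its place. Someone would then have to choose between EE and FAS with the data in hand, and the two sets need different numbers of responses.

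The p-value limits add a second ambiguity. With exactly 36 responses among 173, the count rule rejects the null and a literal reading of the p-value rules does not.

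The membership difference is smaller. The protocol's extra route lets in short-follow-up patients only if they have died, progressed or left the study, and leaves out those still on study. At an early cutoff that pulls the observed rate down.

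**Working it through.** **Inputs.** From protocol 9.2.2.2 and SAP IV.C: null rate 0.15, assumed rate 0.25, looks at 58, 115 and 173 patients; futility at 6 or fewer of 58 and at 20 or fewer of 115; efficacy at 28 or more of 115 and 36 or more of 173; planned enrolment about 190. Assumption: the FAS has 190 patients, that is, everyone planned.

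**Formula.** Exact upper tail: P(X ≥ k | n) = Σ (j = k to n) C(n, j) · 0.15^j · 0.85^(n−j).

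**1. The plan's own figures.**

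| Result | Exact p | Stated limit |
|---|---|---|
| 6/58 | 0.885 | ≥ 0.88 |
| 28/115 | 0.00570 | ≤ 0.0057 |
| 20/115 | 0.2718 | ≥ 0.2718 |
| 36/173 | 0.02454 | ≤ 0.0245, < 0.0245 or < 0.023 |

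The design reproduces. Let X1 ~ Bin(58, p), X2 = X1 + Bin(57, p) and X3 = X2 + Bin(58, p). The design rejects if X1 ≥ 7 and X2 ≥ 28, or if X1 ≥ 7, 21 ≤ X2 ≤ 27 and X3 ≥ 36. With binding futility the type I error is 0.0245 and the power at 25% is 90.7%.

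**2. How likely the final test is.** It is reached when X1 ≥ 7 and 21 ≤ X2 ≤ 27.
- At p = 0.25: crosses at IA2 0.599, reaches the final test 0.364, stops for futility 1 − 0.599 − 0.364 ≈ 0.04.
- At p = 0.15: reaches the final test 0.187.

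By design, then, the path on which the SAP contradicts itself is not a remote one.

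**3. What changes if the FAS replaces EE.** Smallest count with exact p ≤ 0.0245:

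| n | Responses needed |
|---|---|
| 174 to 178 | 37 |
| 179 to 184 | 38 |
| 185 to 190 | 39 |

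At n = 190, 36 responses give p = 0.081, 38 give 0.0375 and 39 give 0.02448. The extra 190 − 173 = 17 patients would have to supply at least 39 − 36 = 3 responders for a just-positive EE result to stay positive.

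**4. The p-value limits at n = 173.** 36/173 gives 0.02454 and 37/173 gives 0.0153.
- Limit 0.023 (protocol 9.2.4.3): 36 fails, 37 is needed.
- Limit 0.0245 taken literally, whether as at most or less than: 36 fails by 0.00004, 37 is needed.
- Limit 0.0246: 36 passes, and for n = 174 to 190 the required counts are the same as under 0.0245.

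Replacing 36 by 37 in the three-look rule lowers the power at 25% from 90.7% to 88.0%, below the stated 90%.

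**5. The membership difference at IA2**, if the protocol wording were followed and every added early exit were a non-responder.
- 28/115 crosses for efficacy; one addition gives 28/116, p = 0.0065, which misses.
- 29/115 survives five additions: 29/120, p = 0.00556.
- 21/115 (p = 0.195) continues, as does 21/121 (p = 0.269); 21/122 (p = 0.282) meets the futility p-value.

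The average effect depends on accrual and exit times that the documents do not give, so none is claimed here.

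**The case against.** The best defence is that the final test is a leftover. The SAP's change log for version 5.0 calls IA2 pivotal and says some analyses done for it will not be repeated. The same restriction to IA2 appears for the differentiation syndrome analysis, the forest plots, the hematologic analyses and the efficacy profiles. On that reading the sponsor trimmed a later report after a decisive IA2 and left the 36/173 text standing. This is probably the intent, but no section states it as a condition, and the documents do not report the IA2 result. The futility branch is covered, because SAP VI.G makes futility stops binding. The continue branch is not.

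A reader might infer that no primary set is named for the final test. That goes too far: SAP VI.I.4 and XI.B name EE without limit. The fault is a contradiction between those lines and the IA2-only lines.

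A reader might also infer that the protocol's EE definition biases the trial's primary result. The documents do not support that. SAP section I says the SAP governs, and its 180-day rule admits patients regardless of outcome. The protocol route tends to lower the rate, so it does not inflate the type I error. The two rules agree, apart from 6 months against 180 days, once every patient has that much follow-up. A flip caused by one patient at exactly 28/115 is a property of any exact boundary.

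On the p-values, it is fair to say that 0.0245 is 0.02454 rounded and that the count was meant to decide. That answers 0.0245 but not 0.023.

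**Conclusion.** The concern holds as an internal contradiction in the SAP and should be fixed. If IA2 neither crossed for efficacy nor met futility, the stated primary test of Cohort 1 could not be produced as the SAP is written. Moving to the FAS would raise the bar from 36 of 173 to 39 of 190, on the assumption of a 190-patient FAS.

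The threshold mismatch is certain and narrow. It matters only at exactly 36 of 173, where 0.023 is plainly not met and 0.0245 is met only after rounding.

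The EE membership difference is a minor harmonisation point. It would matter only if the protocol wording were followed at an IA2 cutoff with some patients still under 6 months from first dose. The SAP says it is based on protocol version 5 while the supplied protocol refers to Version 7/Amendment 6, which may explain the difference.

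None of this shows that a reported result is wrong.

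**What to change.** **SAP**
- In VI.I.4 and XI.B, state that EE is dropped after IA2 only if IA2 crossed a boundary, in which case the 36/173 test is not performed. Otherwise EE stays the primary set for the final CR/CRh test.
- In IV.A, state whether IA2 or the analysis at about 190 patients is the primary analysis.
- In section I, update the protocol version reference.

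**Both documents**
- In protocol 9.2.2.2 and 9.2.4.3 and SAP IV.C and XI.B, use one final rule that 36/173 meets, for example 36 or more of 173 with exact one-sided p ≤ 0.0246. The count rule is unchanged, so the type I error stays at 0.0245 with binding futility.

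**Protocol, at the next planned amendment**
- Remove the early-exit alternative from the EE definition in the synopsis and 9.2.3, so that it matches the SAP's 180-day rule.

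**Cost.** A few SAP sentences, and one EE analysis kept at the final report only if IA2 did not cross a boundary. The protocol edits need IRB/EC approval under protocol 10.6, so they should travel with an amendment that is already planned. No change to sample size or data collection follows.

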9.2.4 Analysis of Clinical Data

9.2.4.1 Demographic and Tumor Characteristics

Baseline demographic and tumor characteristics will be summarized using descriptive statistics (n, mean, median, minimum, maximum, standard deviation [SD], standard error [SE] for continuous variables; n, percent for categorical variables) for each cohort using the cohort to which they were initially assigned, and all patients will be accounted for.

9.2.4.2 Safety Analysis

For DLT-evaluable patients, the summary of DLTs will be provided by dose/dosing schedule for patients in the Phase 1 dose-escalation stage. All other safety analyses will be based on the Safety Set.

For each stage, the safety and tolerability of FT-2102 will be assessed, as evaluated by adverse events, concomitant medication usage, changes from baseline in physical examination, vital signs, clinical laboratory evaluations, and ECG. Safety data will be listed by patient and summarized descriptively.

A treatment-emergent adverse event (TEAE) is defined as an adverse event with onset on or after the start of study drug, or any worsening of a pre-existing medical condition/adverse event with onset on or after the start of study drug and until 28 days after the last dose. For each stage, all adverse events will be coded using MedDRA version 19.1 or higher and summarized by SOC and PT, for each treatment group. Multiple occurrences of an AE are counted only once per patient per SOC and PT for summary tables. Causality of TEAEs (not related, related) and severity (NCI CTCAE version 4.03 or higher) will be summarized by treatment for each stage.

Relationship will be presented by study drug when applicable. All adverse events and serious adverse events (including those with onset or worsening before the start of study drug) will be listed.

Safety laboratory, vital sign, ECG and physical examinations will be summarized by visit. The change from baseline will be presented along with the by-visit summaries. Shifts in laboratory grades, as well as QTcF shifts, will be tabulated. Assessment of changes in liver function tests will be conducted. Abnormal safety assessments will be flagged and separately presented. All safety data will be listed.

Assessment of differentiation syndrome will be conducted as per Montesinos et al. 2009, searching for candidate cases of differentiation syndrome based on AE reports of dyspnea, pulmonary infiltrates, edema, weight gain, pleural effusion, renal failure, hypotension, pericardial effusion, and unexplained fever. Specific methods of identifying candidate cases will be fully described in the Statistical Analysis Plan (SAP).

9.2.4.3 Antileukemic and Antimyelodysplastic Activity

All analysis in the section will be based on patients in the EE Set as the primary analysis, with additional analyses on the FAS, and in some cases the PP Set as supportive.

Primary Efficacy Endpoints and Hypotheses

CR/ CRh Rate

The primary efficacy endpoint for all Phase 2 cohorts, with the exception of Cohort 2, is the CR/CRh rate (defined as bone marrow blasts < 5% with complete (CR) or partial (CRh) hematologic recovery; see Appendix 7 and Appendix 8 for complete definition). The CR/CRh rate will be calculated and presented together with the Clopper-Pearson 95% confidence interval for each cohort.

For Phase 2, Cohort 1, to test the hypothesis that the complete response rate is greater than 15%, a 1-sided exact test for a binomial proportion will be performed. If the exact 1-sided p-value is less than 0.023, the alternative hypothesis will be accepted. This is equivalent to at least 36 CR/CRh responses of 173 EE patients.

For Phase 2, Cohorts 3, 4, and 5 test the hypothesis that the 85% confidence interval for the complete response rate does not include 10%. If there are 5 or more complete responses of the 20 patients in these cohorts, the 85% confidence interval will be greater than 10%, and the alternative hypothesis that the response rate is greater than 10% will be accepted.

Phase 2 Cohorts 6, 7, and 8 are Simon 2-Stage designs and the primary efficacy endpoint will be evaluated via the number of CR/CRh responses stipulated in the design criteria described in Section 9.2.2.

4-Month RFS

The primary endpoint for Phase 2 Cohort 2 is the 4-Month RFS. This will be evaluated by a Simon 2-Stage design described in Section 9.2.2, testing the null hypothesis that the 4-month RFS is < 80%. It is defined as the proportion of patients who have not relapsed or died on or before their 4-month response evaluation. If a patient does not receive a disease response assessment at their 4-month visit but has a subsequent disease response assessment on or after study day 120 that shows non-progression/ non-relapse, they will be evaluated as having achieved 4-month RFS.

Secondary Efficacy Endpoints

CRi, MLFS, Marrow CR, and PR definitions will be derived from the IWG response criteria (see Section 4.3, Appendix 7 and Appendix 8) for AML (2003) and MDS (2006) based on investigator's assessment.

Transfusion independence, defined as the proportion of patients who have received a packed red blood cell or platelet transfusion in the eight weeks prior to first dose of FT-2102 who have a 28-day period during any point on study with no transfusion required. Additionally, the number of patients who are transfusion independent for at least 56 consecutive days will also be summarized. Percent of transfusion independence will be calculated based on the number of patients who were transfusion dependent prior to first dose of FT-2102.

For each cohort, the number and percentage of the best overall response will be presented by response category and by treatment group. Other binomial endpoints including overall response rate (CR + CRh + CRi + MLFS + PR) and rate of responses in the individual response category, will also be analyzed. Number and percentage of patients within each response category will be presented by dose/dosing schedule and visit. Clopper-Pearson 95% confidence intervals will be provided along with the responses.

Overall survival for all cohorts at landmark timepoints will be analyzed.

Time to event data will be analyzed using Kaplan-Meier (KM) methods for each cohort. The median time will be tabulated along with the 95% Brookmeyer Crowley confidence intervals. The estimated probability of survival over time will be plotted as KM curves for each cohort (or by disease type and by treatment).

Detailed considerations for all time to event variables are provided in the SAP.

Additional efficacy analyses will be specified in the SAP.

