Cohort 1 (patients with R/R AML harboring IDH1-R132 mutations): A group sequential design is planned for this cohort with two interim analyses and a final test. One hundred seventy three (173) patients provide 90% power to test the null hypothesis that the true complete response rate (CR + CRh) is 15% or less versus the one-sided alternative hypothesis that the true complete response rate is greater than 15%, with a 2.5% significance level using a one-sided exact test for a binomial proportion, assuming the true response rate is 25%.

Two interim analyses are planned, at approximately 33% and 67% of the information. O'Brien-Fleming stopping boundaries will be used for both alpha and beta adjustments. At the first interim, if $\leq 6/58$ responses are observed (or crude p-value ≥ 0.88), the trial may be stopped early for futility. The first interim analysis will be conducted on the Full Analysis Set (FAS) within Phase 2 Cohort 1. At the first interim analysis, the study is not intended to stop for efficacy. At the second interim analysis, if $\geq 28/115$ responses are observed (or crude p-value is ≤ 0.0057), the trial may stop enrollment for efficacy and if there are 20 or fewer responses (or crude p-value is ≥ 0.2718) the trial may be stopped for futility. The second interim analysis will be conducted

in the Efficacy Evaluable (EE) Set within Phase 2 Cohort 1. In the event of an early stop for efficacy, all enrolled patients would remain on treatment and their long-term efficacy data, such as EFS and OS, will continue to be observed.

If the study is not stopped early for efficacy or futility, at least 173 evaluable patients are planned to be enrolled. A one-sided exact test will be performed. If the one-sided p-value is ≤ 0.0245 , the null hypothesis (the response rate is $\leq 15\%$) will be rejected, and the alternative hypothesis that the response rate is $\geq 15\%$ will be accepted. If exactly 173 patients are evaluable, this is equivalent to 36 or more responses observed.

To account for potential discordance between central and local testing of the IDH1-R132 mutation, approximately 190 patients are planned to be enrolled into this cohort.

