2) Time variable CBD will be transformed to log form (LCBD) as below: LCBD=log(absolute value of CBD + 1)

- 3) A mixed model will be used to predict QOLtdi. The dependent variable is QOLtd; the mixed model will contain random intercept and slope subject effect, and fixed time effect (LCBD). QOLtdi will be predicted at imputed cycles.
- Compute QOLtdi re-transformed to the original scale (QOLback): This should be done by inverting the logistic regression equation.

QOLback = (logit(QOLt) - a)/b = [ln ((QOLt)/(1-QOLt)) - a]/b.

• Round imputed values up to the nearest whole number.

Note that no numerical values will be given after death, but "999" flags will be included to indicate cycles when patient was dead.

D. Multiple Study Centers

No stratification by the study centers will be utilized for analyses of efficacy or safety data.

E. Covariate Adjustment in Primary Analysis

Not planned for the primary analysis.

F. Sample Size Reassessment

No sample size reassessment is planned.

G. Interim Analyses

Interim analyses will be performed for the Phase 2 Cohort 1 and in other applicable Phase 2 cohorts that use two-stage designs, at defined timepoints, as outlined in section IV.C.

- Phase 2 Cohort 1: two interim analyses with 33% and 67% of patients' information respectively
- Phase 2 Cohort 2: with first 11 patients evaluable for response
- Phase 2 Cohort 6: with first 14 patients evaluable for response
- Phase 2 Cohort 7: with first 17 patients evaluable for response

• Phase 2 Cohort 8: with first 7 patients evaluable for response

As a result of these analyses, enrollment in a given cohort may be stopped early for futility, or in Cohort 1 for efficacy as well. Interim analyses that meet stopping criteria for futility are binding.

H. Multiple Comparisons

Alpha is controlled for the primary analysis within each Phase 2 cohorts. Corrections for multiple comparisons are not applied for the secondary or exploratory endpoints, as they are descriptive analyses.

I. Analysis Sets

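### Protocol 9.2.4.3 sets the Cohort 1 final cut-off at p < 0.023 and equates it with 36/173, but 36/173 gives p = 0.02454, and p < 0.023 needs 37 responses.

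*Protocol*

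**What the plan says.** The final success rule for Cohort 1 appears in four places, each time with 36 of 173 as the count.

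- **Protocol 9.2.4.3:** "If the exact 1-sided p-value is less than 0.023, the alternative hypothesis will be accepted", followed by "This is equivalent to at least 36 CR/CRh responses of 173 EE patients".
- **Protocol 9.2.2.2:** reject if the one-sided p-value is at most 0.0245. "If exactly 173 patients are evaluable, this is equivalent to 36 or more responses observed".
- **SAP IV.C:** the same as protocol 9.2.2.2.
- **SAP XI.B:** "If the exact one-sided p-value is less than 0.0245, the alternative hypothesis will be accepted", again equated with 36/173. Here the inequality is strict.

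The second-interim boundaries, in protocol 9.2.2.2 and SAP IV.C, are at least 28/115 for efficacy (p <= 0.0057) and 20/115 or fewer for futility (p >= 0.2718).

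The force of the futility stops also varies. Protocol 9.2.2.2 makes them optional at both looks (at the second, "the trial may be stopped for futility"). SAP IV.C has "the trial may be stopped early for futility" at the first look and "the trial will be stopped for futility" at the second. SAP VI.G then states: "Interim analyses that meet stopping criteria for futility are binding".

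**The concern.** This is the success criterion for the primary endpoint of the largest Phase 2 cohort. If the p-value and the count in adjacent sentences of protocol 9.2.4.3 disagree, a result of 36/173 can be declared either a success or a failure after the data are seen. At least 173 evaluable patients are planned and about 190 enrolled, so the evaluable number may not be 173. At any other number no count is printed and the p-value alone decides, so it matters whether that value is 0.023 or 0.0245.

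Two smaller questions belong with it: whether the other printed p-values admit their own counts, and whether the mixed futility wording affects the type I error.

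**Working it through.** **Inputs** (protocol 9.2.2.2 and 9.2.4.3; SAP IV.C and XI.B): null rate 0.15; alternative 0.25; one-sided exact binomial test; looks at 58, 115 and 173; futility at <= 6/58 and <= 20/115; efficacy at >= 28/115; final count 36.

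**Step 1. Reproduce the plan's design.** I enumerated the three looks exactly: carry forward the binomial distribution at 58, remove totals <= 6, convolve with the next 57 patients, count totals >= 28 as success, remove totals <= 20, convolve with the last 58, and count totals at or above the final cut-off. With both futility stops binding:

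| Final cut-off | Alpha (true rate 15%) | Power (true rate 25%) |
|---|---|---|
| >= 36 | 0.02447 | 90.7% |
| >= 37 | 0.0168 | 88.0% |

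The cut-off of 36 reproduces the stated 2.5% and 90%. The cut-off of 37 falls short of 90%.

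**Step 2. The final p-value.** P(X >= r), X ~ Binomial(173, 0.15):

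- r = 35: 0.038223
- r = 36: 0.024541
- r = 37: 0.015285

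Since 0.024541 > 0.023 > 0.015285, p < 0.023 means at least 37, not 36. A mid-p value (0.0199) or a normal approximation (0.0162; 0.0210 with continuity correction) would put 36/173 below 0.023, but the paragraph specifies the exact test. With 172 patients, 36 responses would pass (0.0226), but the text says 173.

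**Step 3. Other evaluable numbers.** From 174 to 190, the smallest rejecting counts under p < 0.023 and p <= 0.0245 differ at three sizes:

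| Evaluable n | p < 0.023 needs | p <= 0.0245 needs |
|---|---|---|
| 178 | 38 | 37 |
| 184 | 39 | 38 |
| 190 | 40 | 39 |

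**Step 4. How often exactly 36 arises.** Under the same enumeration, the probability of reaching the final test with exactly 36 responses is 2.7% at a true rate of 25% and 6.0% at 20%.

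**Step 5. Rounding of the other cut-offs.** Each printed p-value is rounded to the side that excludes its own count:

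- 36/173 gives 0.024541, above 0.0245. The strict inequality in SAP XI.B excludes it even after rounding to four decimals.
- 28/115 gives 0.005704, above 0.0057.
- 20/115 gives 0.271794, below 0.2718.

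The neighbouring counts are far away (35/173: 0.0382; 27/115: 0.0108; 21/115: 0.1955), so moving the last digit admits no other count.

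**Step 6. Futility wording.** Overall alpha with the final cut-off at 36:

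| Interim 1 stop | Interim 2 stop | Alpha |
|---|---|---|
| binding | binding | 0.02447 |
| ignored | binding | 0.02458 |
| binding | ignored | 0.02574 |
| ignored | ignored | 0.02593 |

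Alpha exceeds 2.5% only if the second-interim stop is ignored.

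**The case against.** The arithmetic in 9.2.4.3 is not open to dispute; the case against concerns its weight.

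- **The SAP governs.** SAP section I says that the SAP controls the analysis, and 0.023 appears nowhere in it. All four statements give the count 36/173. This makes clear which figure is wrong, but the protocol still states it.
- **The test may never be run.** SAP VI.I and the footnote to the analysis-set table in XI.B limit Efficacy Evaluable analyses to the second interim. This stands as a limit on consequence. SAP IV.C and XI.B nevertheless still specify the 173-patient test, so the rule is live on paper.
- **The error is conservative.** A literal 0.023 lowers alpha to 0.0168 and costs 90.7 - 88.0 = 2.7 points of power. True; there is no false-positive risk from this figure.
- **At 173 the contrast with 0.0245 depends on rounding.** Unrounded, 36/173 fails p <= 0.0245 as well. This is correct. The firm contradictions are the one inside 9.2.4.3 and the differing counts at 178, 184 and 190.
- **The last-digit corrections are cosmetic, and futility is a separate matter.** The interim boundaries are printed as counts, and 0.0246 in place of 0.0245 changes no required count from 174 to 190. SAP VI.G already settles futility. Both points are secondary, and worth making only because the same sentences are being edited.

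**Conclusion.** The point holds. Protocol 9.2.4.3 states a final cut-off that its own count does not meet: 36/173 gives p = 0.02454, and p < 0.023 requires 37. The design's stated alpha and power identify 36 as the intended boundary and 0.023 as the error. It should be fixed, though the consequence is narrow: the decision changes only on exactly 36/173, or at the three other evaluable sizes where the p-values imply different counts, and only if the final Efficacy Evaluable test is carried out.

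The p-values for single counts need no assumption beyond the stated test. The alpha and power figures, and the probabilities of ending on 36, treat the three looks as nested samples. That is an approximation, because the first interim uses the Full Analysis Set and the second the Efficacy Evaluable set. The futility wording does not breach alpha under the SAP's binding rule; it is a mismatch between the two documents.

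**What to change.** 1. Delete 0.023 from protocol 9.2.4.3. State one final rule in protocol 9.2.2.2 and 9.2.4.3 and in SAP IV.C and XI.B: reject if at least 36/173 respond, or if p <= 0.0246 for any other evaluable number. With the second look at 115, binding futility and nested looks, overall alpha is then at most 0.02447 for every final number from 173 to 190, the maximum being at 173.
2. In protocol 9.2.2.2 and SAP IV.C, print the second-interim cut-offs as p <= 0.0058 (efficacy, 28/115) and p >= 0.2717 (futility, 20/115), so that each count meets its own p-value.
3. Replace the optional futility wording in protocol 9.2.2.2 (both interims) and SAP IV.C (first interim) with the binding rule of SAP VI.G.

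The cost is digits and wording in those four sections. No patients are added, no analysis is new, and no design boundary moves.
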